8.2.15. Week 58 (Lipid Monitoring Assessment 4 Week Follow-up Visit Procedures)

This visit will be performed only for those subjects who are determined to require additional lipid monitoring at the Week 54 visit. The following procedures will be performed at this visit:

- Record concomitant medications
- Record AEs
- Obtain blood for 10-hour fasted laboratory sample collection for:
 - Lipid panel

Based on this lipid assessment, the third-party Medical Monitor may recommend specific follow-up with the subject's regular physician. Otherwise, all subjects should be advised to follow-up with their regular physician regarding any lipid management needs going forward.

8.2.16. Monitoring of Anti-Drug Antibody Response

Subjects may be contacted to participate in additional optional follow-up visits, if necessary, to monitor anti-drug antibody (ADA) responses.

8.3. Clinical Evaluations

8.3.1. Alcohol Consumption

8.3.1.1. AUDIT-C

During Screening, clinical sites will implement the AUDIT-C, a 3-item alcohol screen that can help identify persons who are hazardous drinkers or have active alcohol use disorders ([Appendix 3](#)). The AUDIT-C is scored on a scale of 0-12. Each AUDIT-C question has 5 answer choices. Points allotted are: a=0 points, b=1 point, c=2 points, d=3 points, e=4 points. For men, a score of 4 or more is considered positive, optimal for identifying hazardous drinking or active alcohol use disorders. For women, a score of 3 or more is considered positive.

However, when the points are all from Question #1 alone (#2 & #3 are zero), it can be assumed that the patient is drinking below recommended limits and it is suggested that the provider review the patient's alcohol intake over the past few months to confirm accuracy.

8.3.1.2. PEth Screening

Subjects with PEth levels ≥ 200 ng/mL AND a positive AUDIT-C at Screening will be excluded from the study.

8.3.1.3. History of Alcohol Consumption

Subjects will also be asked to report their history of alcohol consumption and will be excluded from study participation if they consume ≥ 21 units per week (males) or ≥ 14 units per week (females) for two years prior to Screening and where a unit of alcohol is equivalent to a 12-ounce beer, 4-ounce glass of wine, or a 1-ounce shot of hard liquor.

8.3.2. Liver Biopsy

Subjects who meet the Screening criteria of having a historical liver biopsy if tissue slides are available from within 12 months prior to Screening and are acceptable for central pathologist evaluation will not be required to undergo a liver biopsy. All other subjects will be required to undergo a liver biopsy during the Screening period and prior to randomization according to the study site's local standard of care. Liver biopsy procedures have inherent risks and benefits, and qualified study personnel will discuss these risks and benefits with each potential participant prior to enrollment.

The common procedure for obtaining a liver biopsy sample involves a percutaneous approach using an appropriate gauge needle for sample collection. Other means of obtaining liver biopsy may be used if found appropriate by the study investigator. The primary risks involved include bleeding, pain, and infection at the incision site. Premedication (for example, midazolam can be used, if consistent with local procedures) and post-biopsy care will be according to the study site's standard of care. Adverse events will be collected, and subjects followed as appropriate.

Sites should not perform a local reporting of the NAS or fibrosis score at either Screening or Week 48 in order to maintain the blinding of the primary endpoint. Tissue from all subjects will be collected, prepared, and sent to the Central Study Pathologist for review and determination of NASH. Liver biopsies with histologically confirmed NASH will be further assessed using the NAS established and validated by the NASH CRN (see [Appendix 1](#)), and liver biopsies will also be assessed for fibrosis stage for primary endpoint analysis. The Week 48 biopsy should be obtained before the last dose of aldafermin with a visit window of -7 days.

Sites will collect a liver biopsy sample for subjects who received at least 24 weeks of aldafermin dose and terminate early from the study.

8.3.3. CPA and SHG

CPA (collagen proportional area, with staining) and SHG (Second Harmonic Generation, stain-free) technologies for assessment of fibrosis involve digital pathology system to characterize and accurately quantify collagen fibers area in the liver biopsies. For SHG, when a scan begins with an unstained liver tissue sample, the laser produces two photons (tiny light

particles), which – upon interaction with the collagen fibers – results in the combination of both photons into a single new photon, with twice the energy and therefore twice the frequency and half the wavelength of the initial photons. This is known as SHG, and the detection of SHG signals lead to a high-resolution imaging of collagen fibers within the tissue. Subjects will be assessed using this methodology at baseline and following 48 weeks of treatment with study drug. All testing will be through a central read.

8.3.4. CLDQ NASH

A chronic liver disease questionnaire will be conducted at Screening and on Weeks 24, 48, and 54.

8.3.5. Transient Elastography and Ultrasound Attenuation Rate (Steatosis) using (FibroScan®) Device

A noninvasive device (FibroScan®), where available, will be used for assessing liver stiffness as a measure of fibrosis via elastography (VCTE™) at the Screening Day -56, Weeks 24 and 48. Currently, there are no imaging techniques that can directly detect the specific stage of fibrosis. Most attempt to detect fibrosis indirectly using proposed biomarkers, which include stiffness, diffusion, perfusion, metabolites, and image texture with the leading biomarker being liver stiffness (Younossi 2018). The rationale for using “stiffness” or “elasticity” is that the collagen deposition associated with fibrosis imparts parenchymal rigidity, which on imaging tests is considered as assessing “stiffness” or “elastography.” In addition, the FibroScan® device will provide steatosis information using an ultrasound attenuation rate method (CAP™). For individual subjects, the same FibroScan® device and the same probe (medium [M] or extra large [XL]) must be used for all assessments. Where available, the median Controlled Attenuation Parameter (CAP) value will be recorded from FibroScan® examinations.

8.3.6. Esophagogastroduodenoscopy (EGD)

No evidence of gastroesophageal varices as documented by one of the following assessments:

- a. A historical and locally evaluated EGD obtained within 365 days of screening or
- b. A locally evaluated EGD conducted during the screening period

*If no EGD is available, the latest EGD assessment guidelines during a global pandemic† for patients with compensated cirrhosis (i.e., the expanded Baveno VI criteria, Petta 2018) as follows can be used as a replacement for the EGD to determine eligibility:

- c. Platelet count >110,000/mm³, and a FibroScan® <30 kPa on a M probe or <25 kPa on a XL probe

Note: No more than 30% of the remaining population will be enrolled with the expanded Baveno VI criteria.

† *EGD waived in patients with compensated cirrhosis during a global pandemic per AASLD/ASGE guidelines.*

8.3.7. Pharmacokinetic Blood Sample Collection and Processing

In all subjects, blood samples for PK analysis of aldafermin levels will be collected pre-dose on all treatment visits and 4-hours post dose on Day 1, Week 24, and Week 48. The window for sample collection for the pre-dose time points is \pm 5 minutes.

Subjects participating in the optional PK sub-study will have blood samples collected at the Day 1 and Week 48 visits at the following time points: pre-dose, 0.5, 1, 2, 4, 6, 8, 12, and 24 hours post-dose. The window for sample collection for the pre-dose through 4 hours is \pm 5 minutes, 6-12-hour time points is \pm 30 minutes. The window for sample collection for the 24-hour time points is -2 hours.

Processing, storage, and shipping instructions for these PK blood samples will be presented in the study Lab Manual.

8.3.8. Clinical Laboratory Evaluations

Clinical laboratory evaluations will be collected as outlined in [Section 8](#).

Serum chemistry will include ALT, AST, ALP, bilirubin (direct and total), creatinine, CK, GGT, glucose, HDL, LDL, lipase, total cholesterol, TG, bicarbonate, calcium, BUN, chloride, phosphate, potassium, proteins (albumin, total protein), and sodium. Samples for analysis of ADAs, NAbs will be collected. All NAb samples will be collected as scheduled, and analyzed only if necessary, based on ADA results.

Liver function tests, including AST, ALT, TBL, and ALP, will be compared between Day -56 and Day -42 to assess whether there is worsening of liver disease during screening according to Exclusion #7. An unscheduled visit may be necessary to confirm eligibility if the difference exceeds the allowable percent difference. If performed, unscheduled visit results will be compared to the average of Day -56 and Day -42 results to determine eligibility. If liver function tests are repeated to verify eligibility criteria have been met, there must be a minimum of 14 days (2 weeks) between the Day -42 visit and any unscheduled visit.

Processing, storage, and shipping instructions for the above will be presented in a separate Lab Manual.

8.3.9. C4 Testing

C4 testing will be collected at pre-dose at all treatment visits as well as 4-hours post-dose on Day 1, Week 24, and Week 48.

Subjects participating in the optional PK study will undergo additional C4 testing at the same time points as their PK blood sample collections: Day 1 and Week 48 at pre-dose, and post-dose at 0.5, 1, 2, 4, 6, 8, 12, and 24 hours. The window for sample collection for the pre-dose through 4 hours is \pm 5 minutes, 6-12-hour time points is \pm 30 minutes. The window for sample collection for the 24-hour time points is -2 hours.

8.3.10. Serum Bile Testing

Serum bile acids samples will be collected pre-dose Day 1 and Week 48/early withdrawal.

8.3.11. 12 -Lead Electrocardiograms

12 -lead ECGs will be performed after the subject has been supine for at least 5 minutes, and as outlined in the Schedule of Study Procedures.

8.3.12. Vital Signs

Vital signs (including temperature, respiratory rate, and seated blood pressure and pulse) will be obtained at Screening and at all study visits as outlined in [Section 8](#). Seated blood pressure and pulse will be measured after the subject has been seated for at least 5 minutes.

8.3.13. Physical Examinations and RUQ Pain Assessment

A routine physical examination will be performed at Screening Day -56, Day 1, and Weeks 6, 12, 18, 24, 30, 36, 42, 48, 49 and 54. A specific assessment of RUQ pain will be collected and scored based on 10-point NRS. During the physical examination, the PI directly palpates the RUQ region and asks the subject to provide a number between 0, equal to no pain and 10, being equal to worst pain.

8.3.14. Weight, Body Mass Index, and Waist Circumference Measurements

Subjects will be weighed, BMI calculated, and waist circumference measured at Screening Day -56, Day 1, and Weeks 18, 30, 36, 48 and 54. Formal instructions for recording weight and measuring waist circumference will be provided to sites.

8.3.15. Local Injection-Site Symptom Assessments (LISSA)

Injection site evaluation will be made and documented by the PI or clinic staff using a LISSA.

LISSA evaluations are to be performed at each clinic visit from Day 1 through Week 48.

The LISSA is intended to be a “snapshot” of the ISRs at the time of clinic assessment. The LISSA is not intended to capture ISR data (frequency, severity, duration, etc.) in between clinic visits. As with any other potential AE, investigator judgment should be used as to whether any ISR is recorded as an AE. Mild to Severe Reactions (LISSA Grades 1–3) are reported as AEs at the discretion of the investigator unless standard SAE criteria are met and then must be reported as an SAE. Life-threatening (LISSA Grade 4) meet SAE criteria and must be reported as such.

LISSAs may be performed if necessary and as clinically indicated by the PI to capture ISRs outside of the routine scheduled assessment time points.

The FDA Toxicity Grading Scale will be used to assess any ISRs ([U.S. Department of Health and Human Services 2007](#)). The documented record will include all of the symptoms, severity, and any local reaction (including pain, tenderness, redness, and swelling) and size of injection-site skin reactions identified and observed by the subject or clinic personnel. LISSA scores will be documented on the subject’s CRF.

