3. STUDY OBJECTIVES AND ENDPOINTS

3.1. Primary Objective and Endpoints

The primary objective of this study is to evaluate the efficacy and safety of aldafermin compared to placebo.

1. The primary efficacy endpoint is the change in Enhanced Liver Fibrosis (ELF) score from baseline to Week 48 with aldafermin or matched placebo.
2. The primary safety endpoint is frequency, severity, and timing of adverse events (AEs) and serious adverse events (SAEs).

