8.4. Safety and Other Assessments

8.4.1. Definition of Adverse Events

An AE is defined as any untoward medical occurrence in a patient or clinical investigational subject who has been administered a pharmaceutical product that does not necessarily have a causal relationship with this treatment. A TEAE is an AE that is reported after a dose of study drug.

AEs are all:

- unfavorable changes in general condition
- subjective or objective signs/symptoms
- concomitant diseases or accidents
- clinically relevant adverse changes in laboratory parameters observed in a participant in the course of a clinical study

AEs comprise all disturbances of general health status, subjective and objective disease symptoms (including laboratory abnormalities), and accidents observed in the context of a clinical trial, irrespective of a possible causal relationship with the administration of the trial substance. Events occurring in the framework of a clinical trial during drug-free, and post-treatment periods, or under placebo, are also to be designated as AEs.

All AEs, whether volunteered, elicited, or noted on physical examination, will be recorded throughout the study (i.e., from screening until EOS).

Subjects will be queried for resolution of ongoing AEs or until any unresolved AEs are judged by the PI to have stabilized or if lost to follow-up. Resolution of all AEs will be promptly documented by the clinic in the subject's CRF.

Any pregnancy diagnosed during the study must be reported immediately to the investigator and sponsor, including pregnancy in female partners of male subjects. The pregnancy will be followed to term and/or outcome and this outcome must be reported to the sponsor.

Pregnancy, in and of itself, is not regarded as an AE or SAE unless the birth results in a congenital anomaly/birth defect or there is suspicion that the study treatment may have interfered with the effectiveness of a contraceptive medication or method.

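### Protocol 8.3.15 leaves Grade 1–3 injection-site reactions to the investigator's discretion as AEs while 8.4.1 requires every AE to be recorded, so their count in the primary safety endpoint can be too low and differ between sites

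*Protocol*

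**What the plan says.** Section 3.1 makes the frequency, severity and timing of AEs and SAEs the primary safety endpoint.

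Section 8.4.1 lists subjective and objective signs and symptoms among AEs, irrespective of a causal link, and then states: "All AEs, whether volunteered, elicited, or noted on physical examination, will be recorded throughout the study". It has no exception for injection-site reactions and no severity threshold.

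Section 8.3.15 covers the Local Injection-Site Symptom Assessment (LISSA), done at each clinic visit from Day 1 to Week 48. It gives a different recording rule in two sentences. The first is general: "As with any other potential AE, investigator judgment should be used as to whether any ISR is recorded as an AE". The second is by grade: "Mild to Severe Reactions (LISSA Grades 1–3) are reported as AEs at the discretion of the investigator", with an exception for reactions that meet SAE criteria. Only the top grade is mandatory: "Life-threatening (LISSA Grade 4) meet SAE criteria and must be reported as such". The section also limits the form: "The LISSA is not intended to capture ISR data (frequency, severity, duration, etc.) in between clinic visits". LISSA scores go on the CRF, and extra LISSAs may be done when the investigator sees a clinical reason.

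Section 9.5 tabulates TEAEs and, separately, summarises injection-site reactions by frequency and percentage.

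**The concern.** An event type that arises directly from the daily injection is recorded as an AE under a looser rule than other events, and the primary safety endpoint is built on those records. Two investigators who see the same reaction may both follow 8.3.15, yet one enters an AE and the other does not. With up to about 150 subjects at approximately 80 sites, there are on average fewer than two subjects per site (150 / 80 = 1.9), so site habits cannot average out within a site.

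What is at stake is the AE table for a known local effect of the product. If reactions are more common on active drug, incomplete recording makes the absolute difference from placebo look smaller than it is. An analysis plan cannot recover a between-visit reaction that nobody recorded.

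**Working it through.** The protocol states no figure on this point, so there is nothing to reproduce. The check compares the rules and then illustrates the consequence.

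**1. The two rules side by side.** 8.4.1: a sign or symptom is an AE whatever its cause, and all AEs are recorded. 8.3.15: an injection-site reaction of Grade 1–3 is an AE if the investigator so decides, unless SAE criteria are met. The wording in 8.3.15 that treats this as the usual practice for any potential AE does not match 8.4.1, which grants no such choice.

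**2. How far the discretion reaches.** Under Appendix 2, Grade 3 covers erythema over 10 cm, any narcotic use for pain, and pain that prevents daily activity. Table 9 in 8.4.3 calls an AE severe when the subject cannot continue daily activities. A reaction that fits the protocol's own description of a severe AE may thus be left out of the AE record.

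**3. What LISSA covers.** Scheduled LISSAs: Day 1 and Weeks 2, 6, 12, 18, 24, 30, 36, 42 and 48, which is 10 visits. Daily dosing for 48 weeks gives 48 × 7 = 336 dosing days, and 10 / 336 = 3.0%. This is the share of dosing days with a scheduled assessment, not the share of reactions seen: a reaction that lasts several days can still be present at a visit, and unscheduled LISSAs are allowed. For reactions that have gone by the next visit, AE recording is the main route, and it is the discretionary one.

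**4. Effect on the comparison with placebo.** Illustration only. Inputs: 52 subjects each on placebo and 3 mg (Table 7). Assumed, because the protocol gives no values: true reaction rates p0 on placebo and p3 on 3 mg, and the share r recorded as AEs, equal in both arms because sites are blinded (6.3).

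- Recorded rate = r × true rate
- Recorded risk difference = r × (p3 − p0)
- Recorded risk ratio = (r × p3) / (r × p0) = p3 / p0, unchanged
- Subjects with a reaction not counted = 52 × (1 − r) × true rate
- Power = Φ[(d − 1.96 × SE0) / SE1], where d is the recorded difference, SE0 the pooled and SE1 the unpooled standard error, two-sided 5%

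With r = 0.5:

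| True p0 / p3 | Recorded | Difference, true → recorded (points) | Ratio | Not counted, placebo / 3 mg | Power, r = 1 → r = 0.5 |
|---|---|---|---|---|---|
| 10% / 20% | 5% / 10% | 10 → 5 | 2 | 2.6 / 5.2 | 0.30 → 0.16 |
| 10% / 30% | 5% / 15% | 20 → 10 | 3 | 2.6 / 7.8 | 0.73 → 0.40 |
| 10% / 40% | 5% / 20% | 30 → 15 | 4 | 2.6 / 10.4 | 0.95 → 0.64 |
| 20% / 20% | 10% / 10% | 0 → 0 | 1 | 5.2 / 5.2 | – |

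For 10% against 30%, the recorded difference is 20r points: 15 at r = 0.75, 10 at 0.5 and 5 at 0.25. Power is shown only as a measure of lost information, since 9.5 describes summaries and no test. The last row shows that a larger loss on active drug needs a higher true rate there.

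**5. Evidence for a higher rate on active drug.** Section 2.8 reports more frequent and more severe injection-site reactions at 10 mg in the T2D study. For the NASH study it reports a dose-dependent rise in a group of common TEAEs that includes injection site erythema. But 10 mg is not used here, the pooled incidence levels off from 1 mg (90%, 86% and 86% at 1, 3 and 6 mg), and no injection-site rates by arm are given.

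**6. Link to 7.1.1.** Part i) of that section acts on TEAEs of CTCAE Grade 3 or 4. LISSA grades come from the FDA toxicity scale in Appendix 2. The protocol does not say how one maps to the other.

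**The case against.** The strongest reply is that this is an ordinary and defensible design: local reactions go on a dedicated graded form, and the investigator judges which of them are AEs. LISSA records symptoms, severity and lesion size on the CRF whatever the AE status, extra LISSAs are possible, AEs are asked about at every visit, and 9.5 tabulates injection-site reactions on their own. This stands as mitigation: visit-day reactions are not lost to the safety evaluation. It does not settle the conflict, because the primary safety endpoint is defined on AEs and not on LISSA, and for reactions between visits the decision still rests on the same judgment.

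A reader might infer that the endpoint under-counts a dose-related effect mainly in the active arms. The documents do not support this as a fact. Sites are blinded, a common recording share leaves the risk ratio untouched, and the earlier data suggest a higher rate on active drug without giving it by arm at the doses used here.

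A reader might also infer that a LISSA Grade 3 reaction left out of the AE record escapes the Grade 3 rule in 7.1.1. That would equate two grading scales which the protocol does not equate, and the Grade 3 action there is itself permissive. What remains is that the passages need to be reconciled.

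Nor is recording wholly discretionary: reactions that meet SAE criteria, and all Grade 4 reactions, must be reported.

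**Conclusion.** The contradiction between 8.3.15 and 8.4.1 is real and should be corrected, because it governs what enters a primary endpoint and extends to severe local reactions. AE counts of injection-site reactions can be too low and inconsistent across sites. Absolute differences from placebo would shrink in proportion to the share recorded, provided that reactions are more common on active drug. That condition is plausible from Section 2.8 but not quantified. The size is unknown: every reaction rate and recording share in the illustration is an assumption, as is an equal share in both arms. The LISSA data and the 9.5 summary limit the damage to the AE endpoint itself and to reactions between visits.

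**What to change.** In 8.3.15, replace both the general sentence on investigator judgment and the Grade 1–3 discretion clause with one rule that agrees with 8.4.1. Changing only one of the two would leave the section contradicting itself. The rule should say that injection-site reactions seen at a visit or reported between visits are recorded as AEs; at the very least it should cover all LISSA Grade 3 reactions, with any narrower scope stated as an explicit exception in 8.4.1. It should name the severity scale used for the AE entry. Keep the SAE clause and the Grade 4 sentence as they are.

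Report LISSA results by arm beside the AE endpoint. State how LISSA grades relate to the CTCAE grades used in 7.1.1 so that those passages are reconciled; this point takes no position on the treatment rule there.

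The cost is a short text change, a CRF completion instruction and more mild AE entries under daily injection, some of which will duplicate LISSA data.
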